**9.4. Appendix 4: Derived and Transformed Data**

**9.4.1. General**

Multiple Measurements at One Time Point

 
• Mean of the measurements will be calculated and used in any derivation of summary statistics but if listed, all data will be presented.
 
• If there are two values within a time window the value closest to the target day for that window will be used. If values are the same distance from the target then the mean will be taken.
 
• Subjects having both High and Low values for Normal Ranges at any post-baseline visits for safety parameters will be counted in both the High and Low categories of “Any visit post-baseline” row of related summary tables. This will also be applicable to relevant Potential Clinical Importance summary tables.
 

Study Day

 
• Calculated as the number of days from treatment date :             
 
• Ref Date = Missing → Study Day = Missing
 
• Ref Date < Treatment Date → Study Day = Ref Date – Treatment Date
 
• Ref Date ≥ Treatment Date → Study Day = Ref Date – (Treatment Date) + 1
 
 
 

**9.4.2. Study Population**

Demographics
Age

 
• GSK standard IDSL algorithms will be used for calculating age where birth date will be imputed as follows:             
 
○ Any subject with a missing day will have this imputed as day ‘15’.
 
○ Any subject with a missing date and month will have this imputed as ‘30th June’.
 
 
 
• Birth date will be presented in listings as ‘YYYY’.
 

Body Mass Index (BMI)

 
• Calculated as Weight (kg) / [Height (m)]
 

Extent of Exposure

 
• The cumulative dose will be based on the formula:  Cumulative Dose = Sum of (Number of Days x Total Daily Dose)
 

**9.4.3. Safety**

ECG Parameters
RR Interval

 
• IF ECG values are machine read and either RR interval (msec) is not provided directly, then these can be derived as :              [1] If QTcB is machine read & RR is not provided, then :
 

ECG Parameters
$RR = \left[ \left( \frac{QT}{QT_{cB}} \right)^2 \right] * 1000$

[2] If QTcF is machine read and RR is not provided, then:

$RR = \left[ \left( \frac{QT}{QT_{cF}} \right)^3 \right] * 1000$

 
• If ECGs are manually read, the RR value preceding the measurement QT interval should be a collected value THEN do not derive.
 
• Important Note: Machine read values of RR should not be replaced with re-derived values.
 

Corrected QT Intervals

 
• When not entered directly in the eCRF, corrected QT intervals by Bazett's (QTcB) and Fredericia's (QTcF) formulas will be calculated, in msec, depending on the availability of other measurements.
 
• IF RR interval (msec) is provided then missing QTcB and/or QTcF will be derived as :
 

$QT_{cB} = \frac{QT}{\sqrt{\frac{RR}{1000}}} \qquad \qquad \qquad QT_{cF} = \frac{QT}{\sqrt[3]{\frac{RR}{1000}}}$

 
• Important Note: Machine read values of QTcB and QTcF should not be replaced with re-derived values. If neither machine read QTcB or QTcF are available but QT and RR are collected, then a QTcB and QTcF can be derived however this should be discussed and agreed with the study team and the TLFs must have an appropriate footnote denoting those parameters are derived.
 

Adverse Events
AE's of Special Interest

 
• Liver events
 
• CV events
 
• Infusion site reactions
 
• Potential systemic allergic reactions
 
• GI events
 
• Acetylcholinesterase (AChE) Inhibition
 

## 9.5. Appendix 5: Premature Withdrawals & Handling of Missing Data

### 9.5.1. Premature Withdrawals

Element	Reporting Detail
General	
 
• Subject study completion (i.e. as specified in the protocol) was defined as one who has completed all phases of the study including the follow-up visit.
 
• Withdrawn subjects may be replaced in the study.
 
• All available data from subjects who were withdrawn from the study will be listed and all available planned data will be included in summary tables and figures, unless otherwise specified.
 

### 9.5.2. Handling of Missing Data

Element	Reporting Detail
General	
 
• Missing data occurs when any requested data is not provided, leading to blank fields on the collection instrument : 
 
○ These data will be indicated by the use of a “blank” in subject listing displays. Unless all data for a specific visit are missing in which case the data is excluded from the table.
 
○ Answers such as “Not applicable” and “Not evaluable” are not considered to be missing data and should be displayed as such.
 
 
 

Outliers	
 
• Any subjects excluded from the summaries and/or statistical analyses will be documented along with the reason for exclusion in the clinical study report.
 

#### 9.5.2.1. Handling of Missing Dates

Element	Reporting Detail
General	Partial dates will be displayed as captured in subject listing displays.
Adverse Events	
 
• The eCRF allows for the possibility of partial dates (i.e., only month and year) to be recorded for AE start and end dates; that is, the day of the month may be missing. In such a case, the following conventions will be applied for calculating the time to onset and the duration of the event: 
 
○ Missing Start Day: First of the month will be used unless this is before the start date of study treatment; in this case the study treatment start date will be used and hence the event is considered On-treatment as per Appendix 2: Treatment States and Phases.
 
○ Missing Stop Day: Last day of the month will be used, unless this is after the stop date of study treatment; in this case the study treatment stop date will be used.
 
 
 
• Completely missing start or end dates will remain missing, with no imputation applied. Consequently, time to onset and duration of such events will be missing.
 

Element	Reporting Detail
	
 
• Start or end dates which are completely missing (i.e. no year specified) will remain missing, with no imputation applied.
 

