
Design Features
	
 
• This will be a multi-part study, in which PK requirements must be met (observed mean values: AUC <48 µg•hr/mL and Cmax <14 µg/mL); and safety and tolerability will be reviewed before enrolling subjects into the next part of the study. In Part 1, subjects with normal renal function; subjects with moderate renal impairment; and subjects with severe renal impairment and subjects with ESRD not on hemodialysis will be enrolled. In Part 2 (optional), subjects with normal renal function, subjects with mild renal impairment, and subjects with ESRD on hemodialysis will be enrolled based on the PK, safety, tolerability, and data results of Part 1.
 
• Subjects in Groups A, B, C, D, and E will enter the clinic at Check-in (Day - 1, Period 1) before study drug administration (Day 1, Period 1). In Parts 1 and 2, on Day 1 (Period 1), subjects in Group A, B, C, D, and E will receive a single dose of study drug as follows: gepotidacin 750 mg administered as a 2-hour IV infusion. All subjects will be discharged from the clinic on Day 3 after all scheduled PK and safety assessments have been completed, and will return to the clinic for a Follow-up Visit approximately 10 days (±5 days) after dose administration. The duration of the study (from Screening to the Follow-up
 

Overview of Study Design and Key Features	

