	
Visit) will be approximately 44 days.
 
 
In Part 2 (optional) of the study, subjects in Group F will participate in 2 treatment periods, with dosing in these periods separated by a washout period of at least 7 days. Subjects in Group F will enter the clinic at Check-in (Day -1, Period 1 and Day 7, Period 2) before each study drug administration (Day 1, Period 1 and Day 8, Period 2). On Day 1 (Period 1) and Day 8 (Period 2), subjects in Group F will receive a single dose of study drug as follows: gepotidacin 750 mg administered as a 2-hour IV infusion starting approximately 2 hours before the initiation of the last hemodialysis session of the week (Period 1) and gepotidacin 750 mg administered as a 2-hour IV infusion starting within 2 hours after completion of the last hemodialysis session of the week (Period 2). Subjects in Group F will be discharged from the clinic on Day 10, Period 2 after all scheduled PK and safety assessments have been completed, and will return to the clinic for a Follow-up Visit approximately 10 days (<math>\pm 5</math> days) after the last dose administration in Period 2. The duration of the study (from Screening to the Follow-up Visit) will be approximately 50 days.
 

Dosing	
 
All subjects in Group A, B, C, D, and E will receive a single dose of study drug as follows: gepotidacin 750 mg administered as a 2 hour IV infusion.
 
All subjects in Group F will receive a single dose of study drug as follows: gepotidacin 750 mg administered as a 2 hour IV infusion starting approximately 2 hours before the initiation of the last hemodialysis session of the week (Period 1) and gepotidacin 750 mg administered as a 2 hour IV infusion starting within 2 hours after completion of the last hemodialysis session of the week (Period 2).
 

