#### 9.2.2.2. Treatment States for AE Data

Treatment State	Definition
Pre-Treatment	AE Start Date/Time < Study Treatment Start Date/Time
On-Treatment	If AE onset date/time is on or after treatment start date/time & on or before treatment stop date/time with 2 days lag time. Study Treatment Start Date/Time ≤ AE Start Date/Time ≤ Study Treatment Stop Date/Time + 2 Days
Post-Treatment	If AE onset date/time is after the treatment stop date/time with 2 days lag time. AE Start Date/Time > Study Treatment Stop Date/Time + 2 Days
Onset Time Since 1 st Dose (Days)	If Treatment Start Date/Time > AE Onset Date/Time, = AE Onset Date - Treatment Start Date If Treatment Start Date/Time ≤ AE Onset Date/Time, = AE Onset Date - Treatment Start Date +1 Missing otherwise.
Duration (Days)	AE Resolution Date – AE Onset Date + 1

Treatment State	Definition
Drug-related	If relationship is marked 'YES' on CRF OR value is missing.

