**9.5.2.2. Handling of Partial Dates**

Element	Reporting Detail
Concomitant Medications	
 
• Partial dates for any concomitant medications recorded in the CRF will be imputed using the following convention:                             
 
○ If the partial date is a start date, a '01' will be used for the day and 'Jan' will be used for the month
 
○ If the partial date is a stop date, a '28/29/30/31' will be used for the day (dependent on the month and year) and 'Dec' will be used for the month.
 
 
 
• The recorded partial date will be displayed in listings.
 

Adverse Events	
 
• Any partial dates for adverse events will be raised to data management. If the full date cannot be ascertained, the following assumptions will be made:                             
 
○ If the partial date is a start date, a '01' will be used for the day and 'Jan' will be used for the month.
 
○ However, if these results in a date prior to Week 1 Day 1 and the event could possibly have occurred during treatment from the partial information, then the Week 1 Day 1 date will be assumed to be the start date.
 
○ The AE will then be considered to start on-treatment (worst case).
 
○ If the partial date is a stop date, a '28/29/30/31' will be used for the day (dependent on the month and year) and 'Dec' will be used for the month.
 
 
 
• The recorded partial date will be displayed in listings.
 

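### The cap on a missing AE stop day forces derived durations of one day, zero or less in Groups A to E, and SAP 9.5.2.2 gives a conflicting rule for the same field

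*SAP*

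**What the plan says.** SAP 9.5.2.1 deals with AE dates for which the month and year are known but the day is not, and says that "the following conventions will be applied for calculating the time to onset and the duration of the event". A missing stop day becomes the last day of the month, "unless this is after the stop date of study treatment; in this case the study treatment stop date will be used".

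SAP 9.5.2.2 covers any partial AE date. It is queried with data management. For stop dates that cannot be completed, the rule reads: "a '28/29/30/31' will be used for the day (dependent on the month and year) and 'Dec' will be used for the month". There is no cap at treatment stop. Neither section refers to the other.

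SAP 9.2.2.2 defines AE duration as "AE Resolution Date – AE Onset Date + 1".

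On dosing, SAP 2.3 says that "subjects in Group A, B, C, D, and E will receive a single dose of study drug as follows: gepotidacin 750 mg", given over 2 hours. It also says: "On Day 1 (Period 1) and Day 8 (Period 2), subjects in Group F will receive a single dose of study drug".

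**The concern.** A cap at treatment stop can make sense when treatment lasts weeks. Here treatment lasts two hours, while AEs are collected until the Follow-up Visit, 5 to 15 days after the dose. The end of the recorded month will nearly always fall after treatment stop, so the exception becomes the rule, and the imputed stop date is the infusion day whenever the event began. An event that began later is then recorded as ending before it started.

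On-treatment events are affected as well as late ones. SAP 9.2.2.2 counts onsets up to 2 days after treatment stop as on-treatment, so an on-treatment AE starting on Day 2 or 3 can get a duration of 0 or −1.

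The second problem is reproducibility. Two programmers, each following one of the two sections correctly, would derive different stop dates and durations from the same record.

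**Working it through.** The plan gives no figure to reproduce, so the check is calendar arithmetic on the two rules.

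**Inputs**
- Capped stop-day rule: SAP 9.5.2.1.
- Uncapped stop-date rule: SAP 9.5.2.2.
- Duration = resolution date − onset date + 1: SAP 9.2.2.2.
- Treatment dates: Day 1 for Groups A to E; Days 1 and 8 for Group F (SAP 2.3).
- Follow-up 10 ± 5 days after dosing (SAP 2.3), so at the latest about Day 1 + 15 = Day 16.
- Assumptions: the infusion starts and ends on one calendar date, and the recorded stop month is not before the onset month.

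**Groups A to E, general result.** Let the infusion date be D. Onset on Day k (k ≥ 1) falls on D + k − 1. For k ≥ 2 the stop month must end after D, so the cap applies and the stop date is D. For k = 1 either the cap applies or the month ends on D, and the stop date is again D. Hence

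duration = D − (D + k − 1) + 1 = 2 − k.

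**Example.** Dose on 10 June, stop recorded as June with no day. The uncapped column keeps the recorded month and so ends on 30 June.

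| Onset | Date | Capped (9.5.2.1) | Uncapped (9.5.2.2) |
|---|---|---|---|
| Day 1 | 10 June | 1 | 21 |
| Day 2 | 11 June | 0 | 20 |
| Day 3 | 12 June | −1 | 19 |
| Day 8 | 17 June | −6 | 14 |
| Day 11 | 20 June | −9 | 11 |
| Day 16 | 25 June | −14 | 6 |

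An AE that began the day before dosing stays positive under the cap: 10 − 9 + 1 = 2 days.

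**Literal reading of 9.5.2.2.** The text assigns December without saying that the month must be missing. Onset on 12 June would then end on 31 December: 19 days in June plus 31 + 31 + 30 + 31 + 30 + 31 = 184, or 203 days. The same record therefore yields −1, 19 or 203 days, depending on the section and how it is read.

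**Enumeration.** All 366 dosing dates of a leap year, onset Days 1 to 16 and true durations of 1 to 5 days give 366 × 16 × 5 = 29,280 cases.
- Capped rule, onset Day 1: all 1,830 cases become 1 day, whatever the true duration.
- Capped rule, onset Days 2 to 16: of 27,450 cases, 1,830 are zero, 25,620 are negative and none is positive.
- Uncapped rule with the recorded month kept: none of the 29,280 is zero or negative.

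**Group F.** If treatment stop means the last dose, Day 8, the capped duration is 8 − k + 1 = 9 − k. Onsets on Days 1 to 8 stay positive, Day 9 gives 0 and Day 10 gives −1. If it means the dose of the current period, the Groups A to E pattern recurs after each dose. SAP 9.5.2.1 does not say which applies.

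**The case against.** The strongest reply is that almost nothing planned depends on this. The imputation in 9.5.2.1 serves only time to onset and duration. Both sections keep the recorded partial date in the listings. Treatment state is decided by AE onset, so the stop-date rule cannot move an event between categories. The two AE tables in SAP 9.11.5 cover the mapping of terms and all AEs, and neither is titled as a summary of duration. All of this stands. A derived duration could still appear in an AE listing, but the SAP does not show the shells.

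Few records should reach either rule. SAP 9.5.2.2 queries partial dates before imputing, subjects stay in the clinic to Day 3 and return in person, and Protocol 4.3 plans about 32 subjects in Part 1 and 12 to 24 in optional Part 2. This also stands, although the documents give no expected count.

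It can also be argued that the sections were meant for different cases, a missing day in one and a missing month in the other. The text does not bear this out: 9.5.2.1 describes its own case as a partial date, and 9.5.2.2 claims any partial AE date.

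A reader might infer that every AE with a missing stop day gets a zero or negative duration. The documents do not support that. Day 1 onsets get a truncated but positive 1 day, pre-dose onsets stay positive, and in Group F the answer depends on an unstated choice. Nor do the documents support a claim that events after discharge are the most likely to have partial dates; that is plausible, but nothing in them shows it.

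**Conclusion.** The defect is real but minor. As written, SAP 9.5.2.1 gives a derived AE duration of 2 − k days for onset on Day k in Groups A to E, which is impossible from Day 2 onward, and it conflicts with SAP 9.5.2.2 on the same field with no stated precedence. For Group F the result is undetermined.

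The damage is limited to derived duration for the records, probably few, that still lack a stop day. It would be wrong to infer that the safety conclusions are at risk: recorded dates in listings, treatment state, AE counts and all PK endpoints are untouched.

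The arithmetic assumes that the infusion does not cross midnight. If it did, the stop date would be Day 2 and the formula 3 − k, which is still zero or negative from Day 3.

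**What to change.** Delete the cap at treatment stop in SAP 9.5.2.1, and merge the AE bullets of 9.5.2.1 and 9.5.2.2 into one rule:

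- Query data management first.
- If the stop day is still missing, use the last day of the recorded month, and never a date before AE onset.
- Optionally, go no later than the subject's last study visit or contact. The SAP does not define that date, so define it if the option is used.
- Use December only when the month itself is missing.

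Neither section should be removed whole. Keep the concomitant-medication rule in 9.5.2.2 and the rule for completely missing dates in 9.5.2.1. With the cap gone, the stop-date rule no longer needs to say which Group F dose it refers to.

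The cost is a short SAP text edit. No data collection, table or PK analysis changes.

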**9.5.2.2. Handling of Partial Dates**

Element	Reporting Detail
Concomitant Medications	
 
• Partial dates for any concomitant medications recorded in the CRF will be imputed using the following convention:                             
 
○ If the partial date is a start date, a '01' will be used for the day and 'Jan' will be used for the month
 
○ If the partial date is a stop date, a '28/29/30/31' will be used for the day (dependent on the month and year) and 'Dec' will be used for the month.
 
 
 
• The recorded partial date will be displayed in listings.
 

Adverse Events	
 
• Any partial dates for adverse events will be raised to data management. If the full date cannot be ascertained, the following assumptions will be made:                             
 
○ If the partial date is a start date, a '01' will be used for the day and 'Jan' will be used for the month.
 
○ However, if these results in a date prior to Week 1 Day 1 and the event could possibly have occurred during treatment from the partial information, then the Week 1 Day 1 date will be assumed to be the start date.
 
○ The AE will then be considered to start on-treatment (worst case).
 
○ If the partial date is a stop date, a '28/29/30/31' will be used for the day (dependent on the month and year) and 'Dec' will be used for the month.
 
 
 
• The recorded partial date will be displayed in listings.
 

## 9.6. Appendix 6: Values of Potential Clinical Importance

### 9.6.1. ECG

ECG Parameter	Units	Potential Clinically Important Range	
		Lower	Upper
Absolute			
Absolute QTc Interval	msec	> 450	
		> 450	≤ 479
		≥ 480	≤ 499
		≥ 500	
Absolute PR Interval	msec	< 110	> 220
Absolute QRS Interval	msec	< 75	> 110
Change from Baseline			
Increase from Baseline QTc	msec	> 60	
	msec	> 30	≤ 59
	msec	≥ 60	

### 9.6.2. Vital Signs

Vital Sign Parameter (Absolute)	Units	Potential Clinically Important Range	
		Lower	Upper
Systolic Blood Pressure	mmHg	< 85	> 160
Diastolic Blood Pressure	mmHg	< 45	> 100
Heart Rate	bpm	< 40	> 110

## 9.7. Appendix 7: Division of Microbiology and Infectious Disease Adult Toxicity Tables for Adverse Event Assessment

### 9.7.1. Laboratory Values

Parameter values are converted to use SI units.

HEMATOLOGY				
	Grade 1	Grade 2	Grade 3	Grade 4
Hemoglobin	95 to 105 G/L	80 to 94 G/L	65 to 79 G/L	<65 G/L
Absolute neutrophil count	1.0 to 1.5 $10^9/L$	0.75 to 0.999 $10^9/L$	0.5 to 0.749 $10^9/L$	<0.5 $10^9/L$
Platelets	75 to 99.999 $10^9/L$	50 to 74.999 $10^9/L$	20 to 49.999 $10^9/L$	<20 $10^9/L$
White Blood Cells	11 to 13 $10^9/L$	13 to 15 $10^9/L$	15 to 30 $10^9/L$	>30 or <1 $10^9/L$
% Polymorphonuclear leukocytes + band cells	>80%	90 to 95%	>95%	N/A
Abnormal Fibrinogen	Low: 1 to 2 G/L High: 4 to 6 G/L	Low: <1 G/L High: >6 G/L	Low: <0.5 G/L High: N/A	Fibrinogen associated with gross bleeding or with disseminated coagulation
Fibrin Split Product	0.020 to 0.040 G/L	0.041 to 0.050 G/L	0.051 to 0.060 G/L	>0.060 G/L
Prothrombin Time	1.01 to 1.25 $\times$ ULN	1.26 to 1.5 $\times$ ULN	1.51 to 3.0 $\times$ ULN	>3 $\times$ ULN
Activated Partial Thromboplastin	1.01 to 1.66 $\times$ ULN	1.67 to 2.33 $\times$ ULN	2.34 to 3 $\times$ ULN	>3 $\times$ ULN
Methemoglobin	5.0 to 9.9%	10.0 to 14.9%	15.0 to 19.9%	>20%

N/A = not applicable; ULN = upper limit of normal.

CHEMISTRIES				
	Grade 1	Grade 2	Grade 3	Grade 4
Hyponatremia	130 to 135 MMOL/L	123 to 129 MMOL/L	116 to 122 MMOL/L	<116 MMOL/L or abnormal sodium with mental status changes or seizures
Hypernatremia	146 to 150 MMOL/L	151 to 157 MMOL/L	158 to 165 MMOL/L	>165 MMOL/L or abnormal sodium with mental status changes or seizures
Hypokalemia	3.0 to 3.4 MMOL/L	2.5 to 2.9 MMOL/L	2.0 to 2.4 MMOL/L or intensive replacement therapy of hospitalization required	<2.0 MMOL/L or abnormal potassium with paresis, ileus, or life-threatening arrhythmia
Hyperkalemia	5.6 to 6.0 MMOL/L	6.1 to 6.5 MMOL/L	6.6 to 7.0 MMOL/L	>7.0 MMOL/L or abnormal potassium with life-threatening arrhythmia
Hypoglycemia	3.0 to 3.55 MMOL/L	2.22 to 2.99 MMOL/L	1.67 to 2.21 MMOL/L	<1.67 MMOL/L or abnormal glucose with mental status changes or coma
Hyperglycemia (nonfasting and no prior diabetes)	6.44 to 8.88 MMOL/L	8.89 to 13.88 MMOL/L	13.89 to 27.75 MMOL/L	>27.76 MMOL/L or abnormal glucose with ketoacidosis or seizures
Hypocalcemia (corrected for albumin)	2.10 to 1.95 MMOL/L	1.94 to 1.75 MMOL/L	1.74 to 1.52 MMOL/L	<1.52 MMOL/L or abnormal calcium with life-threatening arrhythmia or tetany
Hypercalcemia (corrected for albumin)	2.64 to 2.87 MMOL/L	2.88 to 3.12	3.13 to 3.37 MMOL/L	>3.37 MMOL/L or abnormal calcium with life-threatening arrhythmia
Hypomagnesemia	0.7 to 0.6 MMOL/L	0.59 to 0.45 MMOL/L	0.44 to 0.3 MMOL/L	<0.3 MMOL/L or abnormal magnesium with life-threatening arrhythmia
Hypophosphatemia	0.7 to 0.8 MMOL/L	0.5 to 0.6 MMOL/L or replacement Rx required	0.3 to 0.4 MMOL/L intensive therapy or hospitalization required	<0.3 MMOL/L or abnormal phosphate with life-threatening arrhythmia
Hyperbilirubinemia (when accompanied by any increase in other liver function test)	1.1 to <1.25 × ULN	1.25 to <1.5 × ULN	1.5 to 1.75 × ULN	>1.75 × ULN
Hyperbilirubinemia (when other liver function tests are in the normal range)	1.1 to <1.5 × ULN	1.5 to <2.0 × ULN	2.0 to 3.0 × ULN	>3.0 × ULN
Blood urea nitrogen	1.25 to 2.5 × ULN	2.6 to 5 × ULN	5.1 to 10 × ULN	>10 × ULN
Hyperuricemia (uric acid)	446 to 595 UMOL/L	596 to 714 UMOL/L	715 to 892 UMOL/L	>892 UMOL/L
Creatinine	1.1 to 1.5 × ULN	1.6 to 3.0 × ULN	3.1 to 6.0 × ULN	>6 × ULN or dialysis required

Rx = therapy; ULN = upper limit of normal.

ENZYMES				
	Grade 1	Grade 2	Grade 3	Grade 4
Aspartate aminotransferase	1.1 to <2.0 × ULN	2.0 to <3.0 × ULN	3.0 to 8.0 × ULN	>8.0 × ULN
Alanine aminotransferase	1.1 to <2.0 × ULN	2.0 to <3.0 × ULN	3.0 to 8.0 × ULN	>8.0 × ULN
Gamma to glutamyl transferase	1.1 to <2.0 × ULN	2.0 to <3.0 × ULN	3.0 to 8.0 × ULN	>8.0 × ULN
Alkaline Phosphatase	1.1 to <2.0 × ULN	2.0 to <3.0 × ULN	3.0 to 8.0 × ULN	>8.0 × ULN
Amylase	1.1 to 1.5 × ULN	1.6 to 2.0 × ULN	2.1 to 5.0 × ULN	>5.1 × ULN
Lipase	1.1 to 1.5 × ULN	1.6 to 2.0 × ULN	2.1 to 5.0 × ULN	>5.1 × ULN

ULN = upper limit of normal.

URINALYSIS				
	Grade 1	Grade 2	Grade 3	Grade 4
Proteinuria	1+ or 200 MG to 1 GM loss/day	2 to 3+ or 1 to 2 GM loss/day	4+ or 2 to 3.5 GM loss/day	Nephrotic syndrome or >3.5 GM loss/day
Hematuria	Microscopic only <10 RBC/HPF	Gross, no clots >10 RBC/HPF	Gross, with or without clots, or red blood cells casts	Obstructive or required transfusion

HPF = high-powered field; RBC = red blood cells.

